4.1.3 DLT evaluability

DLT evaluability is defined as follows:

- Patient completed the first 21-day cycle (DLT assessment period of 21 days)
- Patient received all administrations of nanrilkefusp alfa during the DLT period as per schedule (± 1 day)
- Patient received cetuximab as per schedule (± 1 day)

4.1.4 Study periods

Participation of each patient will consist of the below study periods.

4.1.4.1 Screening

Patients will be screened within a period of not more than 21 days, which will start when the Informed Consent Form (ICF) has been signed and end before day 1 of cycle 1.

4.1.4.2 Treatment

During the treatment period, study interventions will be administered as described in section 6 until any of the criteria for discontinuation of study interventions is met (see section 7.1).

After discontinuation of study interventions, patients will be evaluated at an End of treatment visit. This visit will be scheduled within 7 days (+7 days) after the patients' last dose of nanrilkefusp alfa and/or cetuximab (whichever occurs later).

4.1.4.3 Follow-up

All patients will come to the clinic 30 (± 2) days after their last dose of nanrilkefusp alfa and/or cetuximab (whichever occurs later).

Patients will be contacted 90 (+2) days after their last dose of nanrilkefusp alfa and/or cetuximab (whichever occurs later) and then followed up for survival at 3-month (± 2 weeks) intervals until the end of the study defined in section 4.4.

4.2 Scientific rationale for study design

The AURELIO-05 study is designed as an open-label, single-arm, phase 2 proof-of-concept clinical trial with nanrilkefusp alfa in combination with cetuximab in patients with metastatic colorectal cancer. The study design represents a standard approach in early phase 2 clinical trials where the main aim is to investigate preliminary efficacy signals in an appropriate time frame to enable further clinical evaluation in a subsequent confirmatory clinical trial setting.

The primary endpoint of this study is ORR according to RECIST 1.1. This endpoint has the advantage of being generally assessed earlier and with a smaller sample size compared to time-to-event endpoints. The evaluation of ORR is generally also based on objective and quantitative assessments, i.e., radiological tumor assessments based on the widely accepted RECIST 1.1 response criteria.

In the AURELIO-05 study, the ORR of cetuximab monotherapy in patients with metastatic colorectal cancer with disease progression or intolerance to irinotecan-based and oxaliplatin-based therapy was used as benchmark for the sample size calculation. The target ORR of approximately 37% for the nanrilkefusp alfa + cetuximab combination therapy versus 20% for

cetuximab monotherapy²¹ appears to be an additional clinically relevant benefit for patients with metastatic colorectal cancer, as discussed and confirmed by clinical experts in the colorectal cancer field.

4.3 Justification for dose

4.3.1 Nanrilefusp alfa (SOT101)

In study SC103 (AURELIO-03), 12 µg/kg of nanrilefusp alfa was determined to be the RP2D for both nanrilefusp alfa monotherapy and nanrilefusp alfa combined with pembrolizumab. To ensure that it is safe to administer nanrilefusp alfa at this RP2D together with cetuximab, an initial safety cohort of 3 patients will be treated with cetuximab in combination with 9 µg/kg nanrilefusp alfa, a dose one dose level below the RP2D determined in study SC103 (AURELIO-03). These 3 patients will be closely observed, and safety data collected during the DLT assessment period, i.e., first 21-day treatment cycle, will be evaluated by the ISC. If the safety of nanrilefusp alfa at 9 µg/kg in combination with cetuximab is acceptable, another safety cohort of 3 patients will be treated with cetuximab in combination with 12 µg/kg nanrilefusp alfa, the RP2D determined in study SC103 (AURELIO-03). Safety in the 12 µg/kg cohort will be evaluated by the ISC after the last patient completes the DLT assessment period. If there are no safety concerns in the 12 µg/kg safety cohort, the study will proceed to the main cohort and recruit patients who will receive 12 µg/kg nanrilefusp alfa in combination with cetuximab. If there are safety concerns at the 9 µg/kg and/or 12 µg/kg nanrilefusp alfa safety cohorts, the ISC will decide how to proceed as described in section 4.1.1.

4.3.2 Cetuximab

Cetuximab and its required comedications will be administered as described in section 6.1.

4.4 End of study definition

A patient is considered to have completed the study if s/he has completed all phases of the study including the last follow-up visit or contact in the study (whichever occurs later).

The study will end one year after the last patient's last dose of study treatment (nanrilefusp alfa and/or cetuximab [whichever occurs later]) or 3 years after the last patient has received the first dose of nanrilefusp alfa (whichever occurs earlier).

The sponsor reserves the right to discontinue the study for medical reasons or any other reason at any time. If the study is prematurely terminated or suspended, the sponsor will promptly inform the investigators/institutions, regulatory agencies, and institutional review board (IRB) / independent ethics committee (IEC; in the US) or ethics committee (EC; in the EU) of the termination or suspension and the reason(s) for the termination or suspension.

The investigator reserves the right to discontinue the study for his/her investigational site, should his/her judgment so dictate. If the investigator terminates or suspends the study without prior agreement of the sponsor, the investigator should inform the institution where applicable, and the investigator/institution should promptly inform the sponsor and the IRB/IEC (in the US) / EC (in the EU) and provide the sponsor and the IRB/IEC (in the US) / EC (in the EU) with a detailed written explanation of the termination or suspension.

5 STUDY POPULATION

5.1 Inclusion criteria

Patients will be eligible to be included in the study only if all of the following criteria apply:

Type of patients

1. ≥ 18 years of age on the day of signing informed consent
2. Ability to understand and sign written informed consent to participate in the study
3. Provides written informed consent for the study
4. Life expectancy >6 months

Disease characteristics

5. Histologically or cytologically confirmed advanced and/or metastatic colorectal cancer
6. RAS wild type as confirmed by:
 - locally performed US Food and Drug Administration (FDA)-approved test or an experienced local laboratory using validated test methods for the detection, based on tumor biopsy or
 - locally performed ctDNA assessment including at least mutations in exon 2 (G12D, G12V, G12C, G12S, G12A, G12R, G13D) and determined by a laboratory using validated test methods
 - samples must be taken within 3 months prior to first study administration
7. Patients who are relapsed/refractory or intolerant to prior treatment with irinotecan- and oxaliplatin-containing chemotherapy
8. Have at least one measurable lesion according to RECIST 1.1
9. Eastern Cooperative Oncology Group (ECOG) performance score 0-2
10. Must have recovered from all AEs due to previous therapies to grade ≤ 1 toxicity (excluding alopecia)

Organ function

Have adequate organ function as defined below. Specimens must be collected within 7 days prior to the start of study treatment.

11. Hematology:
 - 11.1. Absolute neutrophil count $\geq 1,500/\mu\text{L}$
 - 11.2. Platelets $\geq 100,000/\mu\text{L}$
 - 11.3. Hemoglobin $\geq 9.0 \text{ g/dL}$ (criteria must be met without packed red blood cell transfusion within the prior 2 weeks; patients can be on stable dose of erythropoietin [≥ 3 months])
12. Renal function: Creatinine clearance rate $\geq 50 \text{ mL/min}$ as calculated using Cockcroft-Gault equation (see section [10.4](#))

13. Hepatic function: ALT/AST $\leq 2.5 \times$ upper limit of normal (ULN) and total bilirubin $\leq 2 \times$ ULN in patients without liver metastasis (benign hereditary hyperbilirubinemias, e.g., Gilbert's syndrome, are permitted if total bilirubin < 3 mg/dL). In patients with liver metastasis, ALT/AST $\leq 5 \times$ ULN is allowed but total bilirubin must be $\leq 2 \times$ ULN.

14. Prothrombin time and activated partial thromboplastin time $\leq 1.5 \times$ ULN

Hepatitis

15. A locally performed hepatitis B (HBV) test is required during screening. Patients who are HBV surface antigen positive are eligible if they have received HBV anti-viral therapy for at least 4 weeks and have undetectable HBV viral load before study entry (ICF signature). Patients should remain on anti-viral therapy throughout study treatment and follow local guidelines for HBV anti-viral therapy post completion of study treatments.

16. A locally performed hepatitis C (HCV) test is required during screening. Patients with history of HCV infection are eligible if HCV viral load is undetectable at screening. Patients must have completed anti-viral therapy at least 4 weeks before study entry (ICF signature).

Special requirements for contraception

17. A female patient is eligible to participate if she is not pregnant, not breastfeeding, and one of the following conditions applies:

17.1. Not a woman of childbearing potential (WOCBP). A WOCBP is defined as fertile, following menarche and until becoming post-menopausal unless permanently sterile. Permanent sterilization methods include hysterectomy, bilateral salpingectomy, and bilateral oophorectomy. A postmenopausal state is defined as no menses for 12 months without an alternative medical cause. A high follicle stimulating hormone level in the postmenopausal range may be used to confirm a post-menopausal state in women not using hormonal contraception or hormonal replacement therapy. However, in the absence of 12 months of amenorrhea, a single follicle stimulating hormone measurement is insufficient.

17.2. A WOCBP who agrees to use a highly effective contraceptive method during the treatment period and for at least 60 days after the last dose of cetuximab or at least 30 days after last dose of nanrilefusp alfa, whichever is later.

- WOCBP can only be included after a negative serum pregnancy test at screening within 7 days before day 1 of cycle 1.
- Highly effective contraception includes:
 - Combined (estrogen- and progestogen-containing) hormonal contraception associated with inhibition of ovulation:
 - Oral
 - Intravaginal
 - Transdermal
 - Progestogen-only hormonal contraception associated with inhibition of ovulation:
 - Oral

- Injectable
- Implantable
- Intrauterine device
- Intrauterine hormone-releasing system
- Bilateral tubal occlusion
- Vasectomized partner provided the partner is the sole sexual partner of the WOCBP trial participant and that the vasectomized partner has received medical assessment of the surgical success.
- Sexual abstinence defined as refraining from heterosexual intercourse during the entire treatment period and for at least 60 days after the last dose of cetuximab or at least 30 days after last dose of nanrilkefusp alfa, whichever is later. The reliability of sexual abstinence needs to be evaluated in relation to the duration of the clinical trial and the preferred and usual lifestyle of the patient.

18. Male patients must agree to use a condom during the treatment period and for at least 60 days after the last dose of cetuximab or at least 30 days after last dose of nanrilkefusp alfa, whichever is later.

5.2 Exclusion criteria

Patients will be excluded from the study if any of the following criteria apply:

Prior/concomitant therapy

1. Prior exposure to drugs that are agonists of IL-2 or IL-15
2. Therapy with cetuximab within 3 months prior to ICF signature or patients who had progressive disease as best response to prior cetuximab-containing regimen
3. Prior systemic anti-cancer therapies, including investigational agents before study entry (ICF signature):
 - 3.1. Less than 3 weeks or 5 half-lives (whichever shorter) for anti-cancer treatments
 - 3.2. Less than 4 weeks from major surgeries and not recovered adequately from the procedure and/or any complications from the surgery
4. Has received more than 4 prior lines of systemic anticancer treatment
5. Has received prior radiotherapy within 2 weeks of the start of study treatments. A 1-week radiation-free period is permitted for palliative radiation (≤ 2 weeks of radiotherapy) to non-central nervous system disease. Patients must have recovered from all radiation-related toxicities and not require corticosteroids.
6. Has received a live or live-attenuated vaccine within 30 days prior to the first dose of study treatments

Prior/concurrent clinical study experience

7. Is currently participating in or has participated in a study of an investigational agent or has used an investigational device within 3 weeks or 5 half-lives (whichever longer) before

study entry (ICF signature). Patients who have entered the follow-up phase of an investigational study may participate as long as it has been 3 weeks or 5 half-lives (whichever longer) after the last dose of the previous investigational agent.

Medical conditions

8. Patients with known BRAF mutations
9. Clinically significant cardiac abnormalities including prior history of any of the following:
 - 9.1. Cardiomyopathy, with left ventricular ejection fraction lower than the lower limit of the institutional normal range at screening
 - 9.2. Congestive heart failure of New York Heart Association grade ≥ 2
 - 9.3. History of clinically significant (i.e., active) atherosclerotic cardiovascular disease, specifically myocardial infarction, unstable angina, cerebrovascular accident within 6 months prior to the first dose of study treatments, and any history of coronary heart disease and clinically significant peripheral and/or carotid artery disease
 - 9.4. Prolongation of QTcF >450 msec; history or family history of congenital long QT syndrome
 - 9.5. Uncontrolled cardiac arrhythmia requiring medication
10. Uncontrolled hypertension defined as systolic blood pressure >160 mmHg, diastolic blood pressure >110 mmHg. Patients with uncontrolled hypertension should be medically managed on a stable regimen to control hypertension prior to study entry (ICF signature).
11. Has a clinical diagnosis of immunodeficiency or is receiving chronic systemic steroid therapy (in dosing exceeding 10 mg daily of prednisone equivalent) or any other form of immunosuppressive therapy within 7 days prior to the first dose of study treatments. Systemic steroid pretreatment prior to cetuximab infusion according to local guidelines is permitted.
12. History of or serology positive for HIV. A locally performed HIV test is required during screening.
13. Has a known additional malignancy that is progressing or has required active treatment within the past 5 years. Patients with basal cell carcinoma of the skin or carcinoma *in situ* (e.g., breast carcinoma, cervical cancer *in situ*) that have undergone potentially curative therapy are eligible.
14. Has known active central nervous system metastases and/or carcinomatous meningitis. Patients with previously treated brain metastases may participate provided they are radiologically stable, i.e., without evidence of progression for at least 4 weeks confirmed during screening.
15. Has an active autoimmune disease that has required systemic treatment in the past 2 years (i.e., with use of disease-modifying agents, corticosteroids, or immunosuppressive drugs). Replacement therapy (e.g., thyroxine, insulin, or physiologic corticosteroid replacement therapy for adrenal or pituitary insufficiency) is not considered a form of systemic treatment and is allowed.
16. Has an active infection requiring systemic therapy

17. Has a history or current evidence of any condition, therapy, or laboratory abnormality that might confound the results of the study, interfere with the patient's participation for the full duration of the study, or is not in the best interest of the patient to participate, in the opinion of the treating investigator
18. Has a known psychiatric or substance abuse disorder that would interfere with the patient's ability to cooperate with the requirements of the study
19. History of hypersensitivity to any component of cetuximab or to compounds of similar biological or chemical composition of nanrilkefusp alfa and/or the excipients contained in the study drug formulations

5.3 Lifestyle considerations

5.3.1 Meals and dietary restrictions

Patients should maintain a normal diet unless modifications are required to manage an AE such as diarrhea, nausea, or vomiting.

5.3.2 Contraception

Nanrilkefusp alfa may have adverse effects on a fetus *in utero*. Furthermore, it is not known if nanrilkefusp alfa has transient adverse effects on the composition of sperm.

Based on findings from animal studies and its mechanism of action, cetuximab can cause fetal harm when administered to a pregnant woman.

Patients should be informed that taking the study treatment may involve risks to the fetus if pregnancy were to occur during the study. If there is any question that a patient of childbearing potential will not reliably comply with the requirements for contraception, that patient should not be entered into the study.

Please also see section [5.1](#).

5.3.3 Use in nursing women

It is unknown whether nanrilkefusp alfa and cetuximab are excreted in human milk. Since many drugs are excreted in human milk, and because of the potential for serious adverse reactions in the nursing infant, patients who are breastfeeding are not eligible for enrollment.

Please also see section [5.1](#).

5.4 Screen failures

Screen failures are defined as patients who consent to participate in the clinical study but are not subsequently entered into the study. A minimal set of screen failure information is required to ensure transparent reporting of screen failure patients to meet the Consolidated Standards of Reporting Trials publishing requirements and to respond to queries from regulatory authorities. Minimal information includes demography, reason for screen failure, and AE/serious AE (SAE).

Patients may be rescreened once.

5.5 Criteria for temporarily delaying enrollment/ administration of study intervention

See section [6.5](#).

6 STUDY INTERVENTIONS AND CONCOMITANT THERAPY

Study intervention is defined as any investigational intervention(s), marketed product(s), placebo, or medical device(s) intended to be administered to a study patient according to the study Protocol.

6.1 Study interventions administered

The interventions to be administered in this study are listed in [Table 6.1](#).

Prophylactic antibiotic therapy (e.g., oral lymecycline or doxycycline) to prevent EGFR inhibitor-related skin toxicities are permitted according to local guidelines.

Prior to the first infusion of cetuximab, patients may receive premedication with an antihistamine and a corticosteroid at least 1 hour prior to administration of cetuximab. This premedication is recommended prior to all subsequent infusions.

Nanrilkefusp alfa subcutaneous injection sites will be rotated to different areas of the body (upper and lower extremities, each of the 4 quadrants of the abdomen) to minimize the summated local effects of nanrilkefusp alfa administration.

The pharmacy manual contains specific instructions for the preparation of the nanrilkefusp alfa dose and cetuximab infusion and administration of nanrilkefusp alfa and cetuximab.

Table 6.1: Study interventions

Intervention name and type	Dosage formulation	Unit dose strength(s)	Dosage level(s)	Route of administration	Regimen/ treatment period	Sourcing
Nanrilkefusp alfa Investigational intervention	Solution for injection	1.3 mg/vial	See section 4.1.1	Subcutaneous	Administration on day 1 (from cycle 2 onwards, ± 1 day), day 2 (± 1 day), day 8 (± 1 day), and day 9 (± 1 day) of each 21-day cycle	Provided centrally
Cetuximab Investigational intervention	Solution for infusion	5 mg/mL	Initial dose: 400 mg/m ² body surface area as intravenous infusion over 120 minutes Subsequent doses: 250 mg/m ² as intravenous infusion over 60 minutes	Intravenous infusion via peripheral or central venous line	Administration on day 1 (from cycle 2 onwards, ± 1 day), day 8 (± 1 day), and day 15 (± 1 day) of each 21-day cycle; on day 1 and day 8, cetuximab infusion will start within 30 minutes after nanrilkefusp alfa administration	Provided centrally

6.2 Preparation, handling, storage, accountability

The investigator or designee must confirm that appropriate temperature conditions have been maintained during transit for all study interventions received and any discrepancies are reported and resolved before use of the study interventions.

Only patients enrolled in the study may receive study interventions and only authorized site staff may supply or administer study interventions. All study interventions must be stored in a secure, environmentally controlled, and monitored (manual or automated) area in accordance with the labeled storage conditions with access limited to the investigator and authorized site staff.

The investigator, institution, or the head of the medical institution (where applicable) is responsible for study intervention accountability, reconciliation, and record maintenance (i.e., receipt, reconciliation, and final disposition records).

Further guidance and information for the final disposition of unused study interventions are provided in the pharmacy manual.

6.3 Measures to minimize bias: randomization and blinding

This is a single-arm clinical trial, randomization and blinding do not apply.

6.4 Study intervention compliance

Treatment for each patient will be recorded during the study.

6.5 Dose modification and toxicity management

6.5.1 Dose modification and toxicity management for nanrilefusp alfa

Dose modification and toxicity management for nanrilefusp alfa for safety reasons, will be discussed on a case-by-case basis between the site and the sponsor's medical monitor. Recommendations for clinical management of cytokine release syndrome are provided in [Table 6.4](#).

To minimize the risk for injection site reaction, subcutaneous injection sites should be rotated to different areas of the body (upper and lower extremities, each of the 4 quadrants of the abdomen) to minimize the summated local effects of nanrilefusp alfa administration.

To minimize the risks associated with shortening of the QT interval, vital signs and electrocardiography (ECG) must be closely monitored as per Protocol and institutional guidelines.

Liver function tests for nanrilefusp alfa toxicity evaluation in this study will include AST, ALT, total bilirubin, and alkaline phosphatase.

Nanrilefusp alfa-related hepatic toxicities should be managed as shown in [Table 6.2](#).

Table 6.2: Management of nanrilkefusp alfa-related hepatic toxicities

Nanrilkefusp alfa-related hepatic toxicity	Severity	Nanrilkefusp alfa dose modification
AST increased or ALT increased, or blood bilirubin increased	Grade 2 with AST or ALT >3 to $\leq 5 \times \text{ULN}$ or total bilirubin >1.5 to $\leq 3 \times \text{ULN}$	Withhold nanrilkefusp alfa Resume nanrilkefusp alfa if increased values return to grade ≤ 1
	Grade ≥ 3 with AST or ALT $>5 \times \text{ULN}$ or total bilirubin $>3 \times \text{ULN}$	Withhold nanrilkefusp alfa Resume nanrilkefusp alfa at one dose level below or reduce by 3 $\mu\text{g}/\text{kg}$ if increased values return to grade ≤ 1 Permanently discontinue nanrilkefusp alfa on second occurrence of grade ≥ 3 hepatic event

Please also refer to the IB, section 6.6 (Management guidelines for identified and potential risks).

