6.5.2 Dose modification and toxicity management for cetuximab

Cetuximab should be reduced, delayed, or discontinued to manage adverse reactions as described in [Table 6.3](#).

Table 6.3: Recommended dose modifications of cetuximab for adverse reactions

Adverse reaction	Severity (CTCAE, version 5.0)	Dose modification
Infusion reactions	Grade 1	Reduce the infusion rate by 50%. Infuse under close supervision.
	Grade 2	Reduce the infusion rate by 50%. Immediately administer treatment for symptoms.
	Grade 3 or 4	Immediately stop infusion and permanently discontinue cetuximab.
Dermatologic toxicities and infectious sequelae (e.g., acneiform rash,	First occurrence; grade 3 or 4	Delay infusion 1 to 2 weeks; if condition improves to grade ≤ 2 , continue at 250 mg/m^2 . If no improvement, discontinue cetuximab permanently.

Adverse reaction	Severity (CTCAE, version 5.0)	Dose modification
mucocutaneous disease)	Second occurrence; grade 3 or 4	Delay infusion 1 to 2 weeks; if condition improves to grade ≤ 2 , continue at 200 mg/m^2 . If no improvement, discontinue cetuximab permanently.
	Third occurrence; grade 3 or 4	Delay infusion 1 to 2 weeks; if condition improves to grade ≤ 2 , continue at 150 mg/m^2 . If no improvement, discontinue cetuximab permanently.
	Fourth occurrence; grade 3 or 4	Discontinue cetuximab permanently.
Pulmonary toxicity	Acute onset or worsening pulmonary symptoms	Delay infusion 1 to 2 weeks; if condition improves, continue at the dose that was being administered at the time of occurrence. If no improvement in 2 weeks or interstitial lung disease is confirmed, discontinue cetuximab permanently.
Ulcerative keratitis	Confirmed diagnosis	Interrupt or discontinue cetuximab permanently.

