7 DISCONTINUATION OF STUDY INTERVENTION AND PATIENT DISCONTINUATION/WITHDRAWAL

7.1 Discontinuation of study intervention

Discontinuation of study treatment does not represent withdrawal from the study.

A patient must be discontinued from study treatment for any of the following reasons:

- Confirmed radiographic disease progression as specified in section [10.2.7](#).
- Clinical disease progression (investigator's assessment)
- AE, namely intercurrent illness or study treatment-related toxicity that would, in the judgment of the investigator, affect assessments of the patient's clinical status to a significant degree or require discontinuation of study treatments
- Pregnancy of the patient
- Concomitant treatment with a prohibited medication
- Initiation of new systemic anti-cancer therapy
- Patient's decision
- Investigator's decision

After discontinuation of nanrilkefusp alfa and/or cetuximab (whichever occurs later), all patients will be followed up in the study as described in section [4.1.4.3](#).

If nanrilkefusp alfa needs to be stopped, patients will discontinue cetuximab as well. Such patients will receive standard of care treatment outside the clinical trial.

If cetuximab needs to be stopped due to an AE or the patient's or investigator's decision, nanrilkefusp alfa treatment can continue until any of the criteria for stopping or discontinuation of study treatment listed above is met. If cetuximab needs to be stopped for any of the reasons listed above except for an AE or the patient's or investigator's decision, nanrilkefusp alfa needs to be discontinued as well.

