8 STUDY ASSESSMENTS AND PROCEDURES

Study procedures and their timing are summarized in the [Schedule of activities](#). Protocol waivers or exemptions are not allowed.

Immediate safety concerns should be discussed with the sponsor immediately upon occurrence or awareness to determine if the patient should continue or discontinue study interventions.

Adherence to the study design requirements, including those specified in the [Schedule of activities](#), is essential and required for study conduct.

All screening evaluations must be completed and reviewed to confirm that potential patients meet all eligibility criteria. The investigator will maintain a screening log to record details of all patients screened and to confirm eligibility or record reasons for screening failure, as applicable.

RAS wild type at screening will be determined by using a locally performed FDA-approved test or an experienced local laboratory using validated test methods for the detection, based on tumor biopsy, or locally performed ctDNA assessment (including at least mutations in exon 2 [G12D, G12V, G12C, G12S, G12A, G12R, G13D]), determined by a laboratory using validated test methods. FDA-approved tests are listed here: <https://www.fda.gov/medical-devices/in-vitro-diagnostics/list-cleared-or-approved-companion-diagnostic-devices-in-vitro-and-imaging-tools>.

Procedures conducted as part of the patient's routine clinical management and obtained before signing of the ICF may be utilized for screening or baseline purposes provided the procedures met the Protocol-specified criteria and were performed within the time frame defined in the [Schedule of activities](#).

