10.1.12 Independent data monitoring committee

Applicable only to the main cohort: An independent data monitoring committee (IDMC) will be established for the main cohort to safeguard the interest and safety of the patients participating in the study and provide independent review and assessment of the efficacy and safety data in a systematic manner.

The IDMC will be tasked with making a recommendation to the sponsor based on their review to continue, modify, or stop recruitment or the trial based on their assessment of efficacy and safety information. The membership, key responsibilities, and the corresponding procedures will be defined in the IDMC Charter.

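### Table 6.2 has no row for the combined liver elevation that section 10.3 calls Hy's law, so after a first related case it withholds nanrilkefusp alfa and then allows it to resume

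*Protocol*

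**What the plan says.** Protocol 6.5.1 directs that hepatic toxicities related to nanrilkefusp alfa be managed by Table 6.2. The table has one event category, "AST increased or ALT increased, or blood bilirubin increased", split by severity:

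- **Grade 2** (AST or ALT >3 to ≤5 x ULN, or total bilirubin >1.5 to ≤3 x ULN): withhold, then resume once values are grade ≤1. No resumption dose is given.
- **Grade ≥3** (AST or ALT >5 x ULN, or total bilirubin >3 x ULN): withhold, then resume one dose level or 3 µg/kg lower once values are grade ≤1. The one permanent stop is in this row: "Permanently discontinue nanrilkefusp alfa on second occurrence of grade" ≥3 hepatic event.

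Protocol 10.3 defines Hy's law as ALT or AST at least 3 x ULN, with total bilirubin above 2 x ULN, ALP below 2 x ULN and no other explanation. It gives 10-50% as the rate of death or transplant when drug-related hepatocellular injury is severe enough to cause jaundice. Section 6.5.1 does not refer to 10.3.

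Protocol 4.1.2 counts a Hy's law case as a DLT, within a list that applies to the safety cohorts.

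The protocol also leaves room for judgment. Dose changes made for safety reasons "will be discussed on a case-by-case basis between the site and the" sponsor's medical monitor (6.5.1). A note under Table 6.2 reads "Please also refer to the IB, section 6.6 (Management guidelines for identified and potential risks".

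**The concern.** Section 10.3 singles out the combination of raised transaminases and raised bilirubin because it signals a much worse outlook than either alone. Table 6.2, which tells the site what to do with the drug, does not recognize the combination. A site that follows the table after recovery would be permitted to give the drug again to a patient whom 10.3 places at high risk from it. If nothing outside the protocol supplies a rule, the decision rests on case-by-case discussion without a written criterion, and similar cases could be handled differently.

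**Working it through.** The point rests on no sample size or error rate. The check is whether any case in the Hy's law range escapes the resume rule of Table 6.2, and whether another section supplies a stop.

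**Step 1: place the 10.3 range in Table 6.2.** Inputs are the cut-offs listed above; ALP <2 x ULN is taken as met and the event as related to nanrilkefusp alfa. Bilirubin above 2 x ULN already exceeds the 1.5 x ULN limit, so every such case is at least in the grade 2 row. It moves to the grade ≥3 row if ALT/AST >5 or bilirubin >3 x ULN. Nothing falls outside the two rows.

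| ALT/AST (x ULN) | Bilirubin (x ULN) | Row | Table's action after a first event has recovered |
|---|---|---|---|
| 3.0 | 2.01 | Grade 2 | resume, no reduction stated |
| 4 | 2.5 | Grade 2 | resume, no reduction stated |
| 5 | 3 | Grade 2 | resume, no reduction stated |
| 5.01 | 2.01 | Grade ≥3 | resume at lower dose |
| 4 | 3.01 | Grade ≥3 | resume at lower dose |
| 8 | 4 | Grade ≥3 | resume at lower dose |

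The lower dose is 12 − 3 = 9 µg/kg or 9 − 3 = 6 µg/kg. A repeat case that stays in the grade 2 row does not trigger the permanent stop either, because that rule counts only grade ≥3 events.

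**Step 2: look for a stop elsewhere.**

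- *4.1.1 and 4.1.2.* A DLT leads to three more patients in the cohort and review by the internal safety committee (ISC). No discontinuation of the affected patient is attached. The rule does not reach the main cohort, which the schema in 1.2 puts at about 46 of 52 patients (52 − 6 = 46; if both safety cohorts expand to six, 52 − 12 = 40).
- *7.1.* There is no liver criterion. The adverse event item applies to toxicity that the investigator judges would affect the patient's "clinical status to a significant degree or require discontinuation of study treatments".
- *Table 6.3 (cetuximab).* There is no hepatic row.
- *Section 8.* Immediate safety concerns "should be discussed with the sponsor immediately upon occurrence or awareness to determine if the patient should continue or discontinue study interventions". This is a process, without a liver threshold.
- *10.1.12.* The IDMC is to "provide independent review and assessment of the efficacy and safety data in a systematic manner". This covers the main cohort as a whole and is not a rule for one patient.
- *SAP 5.6.5.* Hy's law cases are summarized, plotted and listed. No treatment action follows.

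**Step 3: does the protocol write first-event stops at all?** It does for cetuximab. For a grade 3 or 4 infusion reaction, Table 6.3 says "Immediately stop infusion and permanently discontinue cetuximab", although its title presents the contents as recommendations. For diagnosed interstitial lung disease, 6.5.4 makes stopping cetuximab mandatory.

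**The case against.** The strongest reply is that the table does not act alone. Resumption needs recovery to grade ≤1, and 6.5.1 puts dose changes for safety before the medical monitor. Section 7.1 obliges discontinuation when the investigator judges that toxicity requires it. Biochemistry is scheduled on days 1, 2, 8, 9 and 15 of cycle 1 and days 1, 8 and 15 of later cycles, and the table withholds from bilirubin above 1.5 x ULN, below the Hy's law level. In the safety cohorts a case is a DLT, discussed with the investigators and reviewed by the ISC. An automatic stop could also be wrong for this population: 5.1 admits patients with liver metastases at ALT/AST up to 5 x ULN and bilirubin up to 2 x ULN, so some readings will have another cause.

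All of this stands as mitigation, and it makes an unconsidered rechallenge less likely. None of it states what to do with a first unexplained case.

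Three stronger readings are tempting and should not be drawn:

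- *That sites have no Hy's law instruction.* The protocol points to IB section 6.6, which was not available and is a natural place for one.
- *That the protocol ignores Hy's law outside an appendix.* Section 4.1.2 uses it as a DLT.
- *That the size of the harm can be stated.* The documents give no expected incidence. The 10-50% in 10.3 is a general statement about drug-induced injury with jaundice, not an estimate for this trial or for rechallenge after recovery.

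**Conclusion.** The gap in the protocol text is certain: every first related case at the 10.3 thresholds is withheld and may then resume, and no protocol section requires a permanent stop for it. In the main cohort the protocol attaches no action at all to Hy's law. The practical consequence is conditional. It is real if IB section 6.6 is silent; if the IB has a stop, what remains is a table that does not match it. No frequency is claimed. This should be fixed, since the written rule sits badly with the protocol's own account of the risk and the remedy is small. It does not show that the safeguards in place would fail.

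**What to change.** Add a row to Table 6.2 that applies to the safety and main cohorts and overrides the single-parameter rows:

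*ALT/AST ≥3 x ULN with total bilirubin >2 x ULN and ALP <2 x ULN: withhold; inform the medical monitor; work up other causes, including liver metastases and baseline elevation; permanently discontinue nanrilkefusp alfa if no other cause is found; resume only if another cause is established and the medical monitor agrees.*

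Refer to 10.3 from the row and align it with IB section 6.6. Withholding and medical monitor contact are already in 6.5.1; the new content is the cause work-up and the default stop.

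The cost is a protocol amendment of one row and a letter to sites. The laboratory values that trigger the row are already in the biochemistry panel (8.2.5.3). The downside is that under 7.1 a patient who stops nanrilkefusp alfa also stops cetuximab on study. The work-up step is there so that patients whose rise comes from liver metastases do not lose both drugs.
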